14.1.4.5 Programming rules

The following should be used for programming of efficacy results:

14.1.4.5.1 Calculation of 'time to event' variables

Time to event = end date - start date + 1 (in days)

When no post-baseline tumor assessments are available, the date of randomization/start of treatment will be used as end date (duration = 1 day) when time is to be censored at last tumor assessment, i.e. time to event variables can never be negative.

14.1.4.5.2 Incomplete assessment dates

All investigation dates (e.g., X-ray, CT scan) must be completed with day, month and year.

If one or more investigation dates are incomplete but other investigation dates are available, this/these incomplete date(s) are not considered for calculation of the assessment date (and assessment date is calculated as outlined in [Section 14.1.3.2.6](#)). If all measurement dates have no day recorded, the 1st of the month is used.

If the month is not completed, for any of the investigations, the respective assessment will be considered to be at the date which is exactly between previous and following assessment. If a previous and following assessment is not available, this assessment will not be used for any calculation.

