- For subjects who discontinue treatment due to disease progression per RECIST 1.1, at least two additional tumor assessments that are at least 4 weeks apart are recommended (for further central analysis) no less than 4 weeks after the criteria for PD are first met. Tumor assessments after start of new anti-neoplastic therapy are recommended however not required.

Additional imaging assessments may be performed at any time during the study at the investigator's discretion to support the efficacy evaluations for a subject, as necessary. Clinical suspicion of disease progression at any time requires a physical examination and imaging assessments to be performed promptly rather than waiting for the next scheduled imaging assessment.

Each lesion that is measured at baseline must be measured by the same method (either same imaging method or by photography, including a metric ruler) and when possible, by the same local radiologist/physician throughout the study so that the comparison is consistent. The same is true for any new lesions that occur after start of treatment. They should be imaged using the same modality at each subsequent time point. New cutaneous lesions need to be color

photographed including a metric ruler to measure the size of the lesion. If an off-schedule imaging assessment is performed because progression is suspected, subsequent imaging assessments should be performed in accordance with the original imaging schedule.

Combined PET/CT may be used only if the CT is of similar diagnostic quality as a CT performed without PET, including the utilization of IV contrast media. At the discretion of the Investigators, FDG-PET scans may be performed to document progressive disease per RECIST 1.1 ([Appendix 1](#)).

All study imaging (including any off-schedule imaging studies) should be submitted to the designated imaging CRO for quality control.

Following the final PFS analysis:

Efficacy data, other than overall survival, will no longer be collected.

All subjects who discontinue study treatment will immediately be followed for safety assessments and as part of the overall survival follow-up until death, lost to follow-up, or withdrawal of consent as described in [Section 7](#).

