14.1.4.5.3 Incomplete dates for last known date patient alive or death

All dates must be completed with day, month and year. If the day is missing, the 15th of the month will be used for incomplete death dates or dates of last contact.

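### The rule for a death with missing day has no lower bound, and the missing-month rule for tumor assessments is ambiguous and can drop a documented progression

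*Protocol*

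**What the plan says.** The rules are in Appendix 1 of the protocol.

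- **Section 14.1.4.5.1** computes a time as end date minus start date plus 1. With no post-baseline scan, the end date is set to randomization, which gives 1 day, and the sentence closes "i.e. time to event variables can never be negative".
- **Section 14.1.4.5.2** treats incompletely dated tumor assessments in three steps. First, when some investigations are incompletely dated and others are available, "this/these incomplete date(s) are not considered for calculation of the assessment date". Second, when every measurement lacks its day, the 1st of the month is used. Third, "If the month is not completed, for any of the investigations, the respective assessment will be considered to be at the date" halfway between the neighbouring assessments. It then adds: "If a previous and following assessment is not available, this assessment will not be used for any calculation".
- **Section 14.1.4.5.3** reads: "If the day is missing, the 15th of the month will be used for incomplete death dates or dates of last contact". It states no limit in either direction.

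Section 14.1.4 calls this material guidance. Section 14.1.4.5 introduces it as what should be used to program the efficacy results, and Section 14.1.1 says the SAP is to refer to it.

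**The concern.** Both rules feed time-to-event endpoints. The death rule applies to OS and to deaths counted in PFS. Without a floor it can place a death before evidence that the subject was alive, or before randomization. The second case gives a zero or negative time, which cannot be a valid survival time.

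The missing-month rule acts on the date of progression, the main component of the primary endpoint. Its first and third steps overlap when one investigation lacks its month and another is fully dated, and no precedence is given. A progression assessment is often the last one. Under Section 7.2.1.2, further scans are required for subjects treated beyond progression but only recommended for those who stop treatment because of it. A following assessment may therefore not exist, and the fallback then removes the progression.

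**Working it through.** **1. The plan's own figure.** From Section 14.1.4.5.1, time = end - start + 1. With end = start this gives 1 day, as the section states.

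**2. Death with missing day, in the calendar month of randomization.** Section 14.1.4.5.3 sets the end date to the 15th. With randomization on day r, time = 15 - r + 1:

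| r | time (days) |
|---|---|
| 15 | 1 |
| 16 | 0 |
| 17 | -1 |
| 20 | -4 |
| 31 | -15 |

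**3. Death with missing day, in the month of a later known-alive date.** Section 14.1.3.2.7 defines last contact as the last date on which the patient was known to be alive. A subject seen on the 31st and recorded as having died that month is dated dead 31 - 15 = 16 days before that contact.

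How often this happens *among deaths with missing day* depends on assumptions. Take the day of death D as uniform on 1 to 30, and the gap from last contact to death as uniform over the visit interval L. The 15th precedes last contact when the gap is below D - 15. The probability is the sum of (D - 15)/L over D = 16 to 30, divided by 30, which is 120/(30 × L).

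- 4-week visits (Section 7.1.3), L = 28: 120/840 = 0.143.
- 12-week survival calls (Section 7.1.8), L = 84: 120/2520 = 0.048.

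The documents do not say how many deaths lack a day.

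**4. Progression with a missing month.** Section 7.2.1.2 schedules scans at Cycle 4 Day 1 and then every 8 weeks. With 28-day cycles these fall on day 3 × 28 + 1 = 85 and day 85 + 56 = 141. Suppose progression is seen on day 141 by a fully dated CT, and a skin photograph at the same assessment lacks its month.

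- First step of Section 14.1.4.5.2: the photograph's date is ignored and progression is on day 141.
- Third step, read literally, with a following scan 4, 8 or 12 weeks later (day 169, 197 or 225): progression moves to (85 + 169)/2 = 127, (85 + 197)/2 = 141 or (85 + 225)/2 = 155.
- Third step, read literally, with no following scan: the assessment is dropped. If no later event is recorded, the subject is censored on day 85, which is 56 days earlier.

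**5. The same progression with no month on any investigation and no following scan.** The first step cannot apply because nothing is fully dated. The third step applies on either reading, and the progression is dropped.

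**The case against.** The strongest reply concerns the wording. A month not completed for *any* investigation can mean that it is completed for none. The three steps then form a clean sequence, and a fully dated CT always keeps the progression. This is a fair reading, so a reader who infers that one missing month always discards a documented progression goes further than the text. Even on the literal reading, a progression with both neighbours present is re-dated, and a later scan or death may still count as an event. The reply does not reach step 5 of the working. Nor does a later death always restore the event, because Section 10.4.3 censors an event that follows two or more missing or inadequate assessments.

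A reader might also infer direct contradictions with neighbouring rules. The statement about negative times closes the rule for subjects with no post-baseline scan, so only its general wording conflicts with the death rule. Section 10.5.1 sets the censoring date for patients not known to have died and does not address imputed deaths. The fault in the death rule is its impossible output, which needs no second rule to show it.

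Using the 15th for a partial last-contact date might look like credit for unobserved survival. It is an ordinary mid-month convention, and replacing it would be a preference.

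Finally, the material is labelled guidance, Section 14.1.4.5.5 expects standard programs to be adapted, complete dates are required, and the SAP, which is not shown, may add floors and precedence. This limits the reach but does not correct what the protocol states.

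**Conclusion.** The point holds as a minor correction. Followed as written, the death rule can give a date before the last date known alive, and zero or negative times when the death falls in the month of randomization and randomization was on the 16th or later. The missing-month rule is ambiguous when another investigation is fully dated. It drops a progression that has no usable month and no following assessment, whichever way it is read.

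The size is per record: up to 16 days for a death against a known-alive date, and in the example a progression on day 141 turned into censoring on day 85. The 14% and 5% figures apply only to deaths with missing day and rest on the uniform assumptions above. Since complete dates are required, few records should be affected and the effect on the hazard ratio should be small. The final PFS analysis has been done and was not significant (Section 10), and nothing in the protocol suggests that these rules affected it. OS follow-up continues for descriptive analysis, so the death rule is still in use.

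**What to change.** - **Section 14.1.4.5.2:** change *any* to *all* in the missing-month sentence, so that the preceding rule governs whenever at least one investigation is fully dated.
- **Same section:** do not discard an assessment with overall response PD. Take the scan date from the imaging CRO or, failing that, the visit date. The source should exist, since Section 7.2.1.2 says: "All study imaging (including any off-schedule imaging studies) should be submitted to the designated imaging CRO for quality control".
- **Section 14.1.4.5.3:** for a death with missing day, use the later of the 15th and the day after the last date known alive. The imputed date should not precede randomization or, for a death known to have occurred by the data cut-off, fall after it. Leave the last-contact rule as it is.

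For PFS, where the analysis is complete, it is enough to check whether any record met the missing-month rule and to report the answer. The cost is a few lines in Appendix 1 or the SAP, the matching program changes, and a reconciliation of partial scan dates with the imaging vendor. No new patient data are needed.

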14.1.4.5.3 Incomplete dates for last known date patient alive or death

All dates must be completed with day, month and year. If the day is missing, the 15th of the month will be used for incomplete death dates or dates of last contact.

14.1.4.5.4 Non-target lesion response

If no non-target lesions are identified at baseline (and therefore not followed throughout the study), the non-target lesion response at each assessment will be considered 'not applicable (NA)'.

14.1.4.5.5 Study/project specific programming

The standard analysis programs need to be adapted for each study/project.

14.1.4.5.6 Censoring reason

In order to summarize the various reasons for censoring, the following categories will be calculated for each time to event variable based on the treatment completion page, the study evaluation completion page and the survival page.

For survival the following censoring reasons are possible:

- Alive
- Lost to follow-up

For PFS and TTP (and therefore duration of responses) the following censoring reasons are possible:

- Ongoing without event
- Lost to follow-up
- Withdrew consent
- Adequate assessment no longer available*
- Event documented after two or more missing tumor assessments (optional, see [Table 14-4](#))

- Death due to reason other than underlying cancer (*only used for TTP and duration of response*)
- Initiation of new anti-cancer therapy

* Adequate assessment is defined in [Section 14.1.3.2.6](#). This reason is applicable when adequate evaluations are missing for a specified period prior to data cut-off (or prior to any other censoring reason) corresponding to the unavailability of two or more planned tumor assessments prior to the cut-off date. The following clarifications concerning this reason should also be noted:

- This may be when there has been a definite decision to stop evaluation (e.g., reason="Sponsor decision" on study evaluation completion page), when patients are not followed for progression after treatment completion or when only UNK assessments are available just prior to data cut-off).
- The reason "Adequate assessment no longer available" also prevails in situations when another censoring reason (e.g., withdrawal of consent, loss to follow-up or alternative anti-cancer therapy) has occurred more than the specified period following the last adequate assessment.
- This reason will also be used to censor in case of no baseline assessment.

14.2.1 Introduction

This appendix provides details of the statistical model, the derivation of prior distributions from historical data, and the results of the Bayesian analyses and respective dosing decisions for hypothetical data scenarios.

14.2.2 Statistical model

For each of the k dosing regimens ($k = 1, 2, 3$), a separate statistical model will comprise of single-agent toxicity parts and interaction parts to describe both two-way and three-way drug safety interactions.

- Model 1 will incorporate DLT data from the first 8 weeks of triple combination treatment in cohort 1 (400 mg i.v. PDR001 Q4W + 150 mg BID dabrafenib + 2 mg QD trametinib)
- Model 2 will incorporate DLT data from the first 8 weeks of triple combination treatment in cohort -1a (400 mg i.v. PDR001 Q8W + 150 mg BID dabrafenib + 2 mg QD trametinib)
- Model 3 will incorporate DLT data from the first 8 weeks of triple combination treatment in cohort -1b (4 weeks run-in of 150 mg BID dabrafenib + 2 mg QD trametinib, followed by 400 mg i.v. PDR001 Q4W + 150 mg BID dabrafenib + 2 mg QD trametinib)

14.2.2.1 Single agent parts

Let $\pi_{1k}(d_1)$ be the risk of DLT for dabrafenib given as a single agent BID at dose d_1 for the k th model ($k = 1, 2, 3$); $\pi_{2k}(d_2)$ be the risk of DLT for trametinib given as a single agent QD at dose d_2 for the k th model; and $\pi_{3k}(d_3)$ be the risk of DLT for PDR001 given as a single agent Q4W at dose d_3 for the k th model. These single agent dose-DLT models are logistic:

$$\text{Dabrafenib: } \text{logit}(\pi_{1k}(d_1)) = \log(\alpha_{1k}) + \beta_{1k} \log(d_1/150)$$

$$\text{Trametinib: } \text{logit}(\pi_{2k}(d_2)) = \log(\alpha_{2k}) + \beta_{2k} \log(d_2/2)$$

$$\text{PDR001: } \text{logit}(\pi_{3k}(d_3)) = \log(\alpha_{3k}) + \beta_{3k} \log(d_3/400)$$

where 150 mg, 2 mg, and 400 mg are used to scale the doses of dabrafenib, trametinib, and PDR001, respectively. Hence, for the k th model, α_{1k} , α_{2k} , and α_{3k} (>0) are the single agent odds of a DLT at 150 mg BID, 2 mg QD, and 400 mg Q4W, respectively; and β_{1k} , β_{2k} , and β_{3k} (>0) are the increase in the log-odds of a DLT by a unit increase in log-dose.

14.2.2.2 Interaction

Under no interaction, the risk of a DLT for the k th model ($k = 1, 2, 3$) at dose d_1 of dabrafenib, dose d_2 of trametinib, and dose d_3 of PDR001 is:

$$\pi_{123k}^0(d_1, d_2, d_3) = 1 - (1 - \pi_{1k}(d_1))(1 - \pi_{2k}(d_2))(1 - \pi_{3k}(d_3))$$

To allow for interaction between dabrafenib, trametinib, and PDR001, odds multipliers are introduced:

η_{12k}	Two-way interaction between dabrafenib and trametinib
η_{13k}	Two-way interaction between dabrafenib and PDR001
η_{23k}	Two-way interaction between trametinib and PDR001
η_{123k}	Three-way interaction between dabrafenib, trametinib, and PDR001

The risk of DLT for combination dose (d_1, d_2, d_3) is then given by:

$$\begin{aligned} \text{odds}(\pi_{123k}(d_1, d_2, d_3)) &= \exp(\eta_{12k} \times d_1/150 \times d_2/2) \\ &\times \exp(\eta_{13k} \times d_1/150 \times d_3/400) \\ &\times \exp(\eta_{23k} \times d_2/2 \times d_3/400) \\ &\times \exp(\eta_{123k} \times d_1/150 \times d_2/2 \times d_3/400) \\ &\times \text{odds}(\pi_{123k}^0(d_1, d_2, d_3)) \end{aligned}$$

where $\text{odds}(\pi) = \pi / (1 - \pi)$; η_{ijk} is the k th model log-odds ratio between the interaction and no interaction model at the reference dose for treatments i and j and a zero dose of the third treatment; and $(\eta_{12k} + \eta_{23k} + \eta_{32k} + \eta_{123k})$ is the k th model log-odds ratio between the interaction and no interaction model, at the reference dose for all three treatments. Here $\eta_{ijk} = 0$ corresponds to no interaction, with $\eta_{ijk} > 0$ and $\eta_{ijk} < 0$ representing synergistic and antagonistic toxicity, respectively.

14.2.3 Prior specifications

The Bayesian approach requires the specification of prior distributions for all model parameters which include, for the k th model ($k = 1, 2, 3$), the single agent parameters $\log(\alpha_{1k})$ and $\log(\beta_{1k})$ for dabrafenib, $\log(\alpha_{2k})$ and $\log(\beta_{2k})$ for trametinib, $\log(\alpha_{3k})$ and $\log(\beta_{3k})$ for PDR001, and interaction parameters η_{12k} , η_{13k} , η_{23k} , and η_{123k} . A meta-analytic-predictive (MAP) approach is used to derive a prior distribution for the single agent model parameters based upon available DLT data. For dabrafenib and trametinib, 100% MAP priors will be used. For PDR001, this is then robustified by creating a mixture prior including both a component derived from the MAP prior and a weakly informative robustification component. This robustification allows for the possibility that the dose/toxicity relationship for PDR001 in combination differs substantially from that of the single agent.

14.2.3.1 Prior distribution for the logistic parameters

Description of the meta-analytic-predictive (MAP) approach

The aim of the MAP approach is to derive a prior distribution from the logistic parameters ($\log(\alpha^*)$, $\log(\beta^*)$) of the new trial using DLT data from historical studies.

Gp

The corresponding probability of a DLT is π_{ds} . The model specifications for the derivation of the MAP prior are as follows:

$$\begin{aligned} r_{ds} \mid \pi_{ds} &\sim \text{Bin}(\pi_{ds}, n_{ds}) \\ \text{logit}(\pi_{ds}) &= \log(\alpha_s) + \beta_s \log(d/d_{\text{ref}}) \\ (\log(\alpha_s), \log(\beta_s)) \mid \mu, \psi &\sim \text{BVN}(\mu, \psi), s = 1, \dots, S \\ (\log(\alpha^*), \log(\beta^*)) \mid \mu, \psi &\sim \text{BVN}(\mu, \psi) \end{aligned}$$

where d_{ref} is the reference dose. The parameters $\mu = (\mu_1, \mu_2)$ and ψ are the mean and between-trial covariance matrix for the logistic parameters, the latter with standard deviations τ_1 and τ_2 and correlation ρ . The parameters τ_1 and τ_2 quantify the degree of between-trial heterogeneity. The following priors are used for these parameters:

- normal priors for μ_1 and μ_2 ,
- log-normal priors for τ_1 and τ_2 , and
- a uniform prior for ρ

The MAP prior for single agent model parameters in the new trial, $(\log(\alpha^*), \log(\beta^*))$, is the predictive distribution

$$(\log(\alpha^*), \log(\beta^*)) \mid (r_{ds}, n_{ds}; s = 1, \dots, S)$$

Since the predictive distribution is not available analytically, MCMC is used to simulate values from this distribution. This is implemented using JAGS version 4.1.0.

Single agent dabrafenib:

The prior distributions for the k th model ($k = 1, 2, 3$) of dabrafenib single agent BLRM model parameters $(\log(\alpha_{1k}), \log(\beta_{1k}))$ are based 100% on MAP.

MAP component for dabrafenib

For the MAP model for dabrafenib, reference dose $d_{ref} = 150$ mg (BID) is used, and data from $S = 1$ history study are available.

Weakly informative normal priors are assumed for μ_{11k} and μ_{12k} , with means corresponding to an assumed 10% risk of DLT at the reference dose of 150 mg, and a double in dose leading to a doubling in the odds of a DLT, respectively. Priors for τ_{11k} and τ_{12} are assigned such that (1) their medians correspond to moderate between-trial heterogeneity, and (2) their uncertainty (95% prior interval) cover plausible between-trial standard deviations ([Neuenschwander 2014](#)).

[figure not shown]
The prior distributions for the model used for deriving the MAP priors for dabrafenib are specified in [Table 14-5](#).

Table 14-5 Prior distributions for the parameters of the MAP model used to derive the prior for the single agent dabrafenib model parameters

Parameter	Prior distribution
μ_{11k}	N(mean = logit(0.1), sd = 2)
μ_{12k}	N(mean = logit(0.5), sd=1)
τ_{11k}	log-normal(mean = 0.250, sd = log(2)/1.96)
τ_{12k}	log-normal(mean = 0.125, sd = log(2)/1.96)
ρ_{1k}	uniform(-1,1)

Historical data for dabrafenib

The dose-DLT data of dabrafenib single agent from the following clinical study are considered as relevant information ([Table 14-6](#)). Only BID dosing data from this study were used to derive the prior distribution for the BLRM parameters $(\log(\alpha_{1k}), \log(\beta_{1k}))$ for model k ($k = 1, 2, 3$).

- **BRF112680:** open-label, multi-center, phase I dose-escalation study to investigate the safety, pharmacokinetics, and pharmacodynamics of dabrafenib in subjects with solid tumors or BRAF-mutation positive melanoma

The DLT observation window in the phase I dose escalation part of this trial was 3 weeks.

Table 14-6 Historical data from dabrafenib single agent clinical study

Dose level	Number of evaluable patients	Number of DLTs
35 mg BID	4	0
70 mg BID	4	0
100 mg BID	6	0
150 mg BID	6	0
200 mg BID	7	1
350 mg BID	6	1

Single agent trametinib:

The prior distributions for the kth model ($k = 1, 2, 3$) of trametinib single agent BLRM model parameters ($\log(\alpha_{2k}), \log(\beta_{2k})$) are based 100% on MAP.

MAP component for trametinib

For the MAP model for trametinib, reference dose $d_{\text{ref}} = 2$ mg (QD) is used, and data from $S = 1$ history study are available.

Weakly informative normal priors are assumed for μ_{21k} and μ_{22k} , with means corresponding to an assumed 10% risk of DLT at the reference dose of 2 mg, and a double in dose leading to a doubling in the odds of a DLT, respectively. Priors for τ_{21k} and τ_{22k} are assigned such that (1) their medians correspond to moderate between-trial heterogeneity, and (2) their uncertainty (95% prior interval) cover plausible between-trial standard deviations.

[figure not shown]
The prior distributions for the model used for deriving the MAP priors for trametinib are specified in [Table 14-7](#).

Table 14-7 Prior distributions for the parameters of the MAP model used to derive the prior for the single agent trametinib model parameters

Parameter	Prior distribution
μ_{21k}	$N(\text{mean} = \text{logit}(0.1), \text{sd} = 2)$
μ_{22k}	$N(\text{mean} = \text{logit}(0.5), \text{sd}=1)$
τ_{21k}	$\text{log-normal}(\text{mean} = 0.250, \text{sd} = \text{log}(2)/1.96)$
τ_{22k}	$\text{log-normal}(\text{mean} = 0.125, \text{sd} = \text{log}(2)/1.96)$
ρ_{2k}	$\text{uniform}(-1,1)$

Historical data for trametinib

The dose-DLT data of trametinib single agent from the following clinical study are considered as relevant information ([Table 14-8](#)) and were used to derive the prior distribution for the BLRM parameters ($\log(\alpha_{2k}), \log(\beta_{2k})$) for model k ($k = 1, 2, 3$).

- **MEK111054:** open-label, multi-center, phase I dose-escalation study to investigate the safety, pharmacokinetics, and pharmacodynamics of trametinib in subjects with solid tumors or BRAF-mutation positive melanoma

The DLT observation window in the phase I dose escalation part of this trial was 4 weeks.

Table 14-8 Historical data from trametinib single agent clinical study

Dose level	Number of evaluable patients	Number of DLTs
2.5 mg QD	9	0
3 mg QD	12	0
4 mg QD	3	1

Single agent PDR001 Q4W:

The prior distributions for the k th model ($k = 1, 2, 3$) of PDR001 Q4W single agent BLRM model parameters ($\log(\alpha_{3k}), \log(\beta_{3k})$) are a mixture of two components: a MAP component and a robustification component used to allow for a dose/toxicity relationship for PDR001 in a combination that differs substantially from that in single agent. The components form a mixture prior with respective weights (0.95, 0.05).

MAP component for PDR001 for model 1 (dosing regimen 1)

For the MAP model for dosing regimen 1 of PDR001, reference dose $d_{\text{ref}} = 400$ mg (Q4W) is used, and data from $S = 1$ historical study are available.

Weakly informative normal priors are assumed for μ_{311} and μ_{321} , with means corresponding to an assumed 10% risk of DLT at the reference dose of 400 mg, and a double in dose leading to a doubling in the odds of a DLT, respectively. Priors for τ_{311} and τ_{321} are assigned such that (1) their medians correspond to moderate between-trial heterogeneity, and (2) their uncertainty (95% prior interval) cover plausible between-trial standard deviations.

The prior distributions for the model used for deriving the MAP priors for dosing regimen 1 of PDR001 are specified in [Table 14-9](#).

Table 14-9 Prior distributions for the parameters of the MAP model used to derive the prior for the single agent PDR001 model parameters for model 1 (dosing regimen 1)

Parameter	Prior distribution
μ_{311}	$N(\text{mean} = \text{logit}(0.1), \text{sd} = 2)$
μ_{321}	$N(\text{mean} = \text{logit}(0.5), \text{sd}=1)$
τ_{311}	$\text{log-normal}(\text{mean} = 0.250, \text{sd} = \log(2)/1.96)$
τ_{321}	$\text{log-normal}(\text{mean} = 0.125, \text{sd} = \log(2)/1.96)$
ρ_{31}	$\text{uniform}(-1, 1)$

MAP component for PDR001 for model 2 (dosing regimen -1a)

For the MAP model for dosing regimen -1a of PDR001, reference dose $d_{\text{ref}} = 400$ mg (Q4W) is used, and data from $S = 1$ historical study are available.

Weakly informative normal priors are assumed for μ_{312} and μ_{322} , with means corresponding to an assumed 10% risk of DLT at the reference dose of 400 mg, and a double in dose leading to a doubling in the odds of a DLT, respectively. Priors for τ_{312} and τ_{322} are assigned such that (1) their medians correspond to substantial between-trial heterogeneity, and (2) their uncertainty (95% prior interval) cover plausible between-trial standard deviations. As less is information is known about Q8W versus Q4W dosing of PDR001, substantial between-trial heterogeneity is assumed for PDR001 in dosing regimen -1a. The prior distributions for the model used for deriving the MAP priors for dosing regimen -1a of PDR001 are specified in [Table 14-10](#).

Table 14-10 Prior distributions for the parameters of the MAP model used to derive the prior for the single agent PDR001 model parameters for model 2 (dosing regimen -1a)

Parameter	Prior distribution
μ_{312}	N(mean = logit(0.1), sd = 2)
μ_{322}	N(mean = logit(0.5), sd=1)
τ_{312}	log-normal(mean = 0.50, sd = log(2)/1.96)
τ_{322}	log-normal(mean = 0.25, sd = log(2)/1.96)
ρ_{32}	uniform(-1,1)

MAP component for PDR001 for model 3 (dosing regimen -1b)

For the MAP model for dosing regimen -1b of PDR001, reference dose $d_{ref} = 400$ mg (Q4W) is used, and data from $S = 1$ historical study are available.

Weakly informative normal priors are assumed for μ_{313} and μ_{323} , with means corresponding to an assumed 10% risk of DLT at the reference dose of 400 mg, and a double in dose leading to a doubling in the odds of a DLT, respectively. Priors for τ_{313} and τ_{323} are assigned such that (1) their medians correspond to substantial between-trial heterogeneity, and (2) their uncertainty (95% prior interval) cover plausible between-trial standard deviations. As less is information is known about Q4W dosing of PDR001 after a 4 week run-in of dabrafenib and trametinib versus immediate Q4W dosing, substantial between-trial heterogeneity is assumed for PDR001 in dosing regimen -1b. The prior distributions for the model used for deriving the MAP priors for dosing regimen -1b of PDR001 are specified in [Table 14-11](#).

Table 14-11 Prior distributions for the parameters of the MAP model used to derive the prior for the single agent PDR001 model parameters for model 3 (dosing regimen -1b)

Parameter	Prior distribution
μ_{313}	N(mean = logit(0.1), sd = 2)
μ_{323}	N(mean = logit(0.5), sd=1)
τ_{313}	log-normal(mean = 0.50, sd = log(2)/1.96)
τ_{323}	log-normal(mean = 0.25, sd = log(2)/1.96)
ρ_{33}	uniform(-1,1)

Historical data for PDR001

The dose-DLT data of PDR001 single agent from the following clinical study are considered as relevant information (Table 14-12) and were used to derive the prior distribution for the BLRM parameters ($\log(\alpha_{3k})$, $\log(\beta_{3k})$) for model k ($k = 1, 2, 3$).

- **CPDR001X201:** open-label, multi-center, phase I/II study of the safety and efficacy of PDR001 administered to patients with advanced malignancies

The DLT observation window in the phase I dose escalation part of this trial was 4 weeks. A review of AE records of the patients did not indicate any significant additional toxicity in the 2nd cycle of treatment, suggesting data from the 1 cycle DLT evaluation period of study CPDR001X2101 is also information for a 2 cycle DLT evaluation period. Assuming the average weight of a patients is 80 kg, each dose level in the historical data d_{Q4W} [mg/kg] can be converted to a flat dose level, using the following:

$$d_{Q4W} \text{ [mg]} = d_{Q4W}[\text{mg/kg}] * 80[\text{kg}]$$

Table 14-12 Historical data from PDR001 Q4W single agent clinical study

Dosing schedule	Dose level (mg/kg)	Converted to dose level in Q4W (mg)	Number of evaluable patients	Number of DLTs
q4w	3	240	6	0
q4w	5	400	10	0

Robustification component of PDR001

To take into account the potential situation that PDR001 in combination is substantially more toxic than when administered as single agent, and that the longer DLT period of 8 weeks (56 days) may increase the chance of experiencing toxicity, a second prior component with vague bivariate normal distribution centered around a higher toxicity is added to improve the robustness of the final prior. The parameters of this weakly information prior distribution are described below:

- The mean ($\log(\alpha_{3k})$, $\log(\beta_{3k})$) = (logit(0.33), 0), i.e. the median DLT rate at the reference dose (400 mg), was assumed to be 0.33 and doubling in dose was assumed to double odds of DLT.
- To complete the specification, the prior standard deviation, $sd(\log(\alpha^{3k}), \log(\beta^{3k}))$, was set equal to (2,1) which allows for considerable prior uncertainty for the dose/toxicity profile.
- The correlation, $\text{corr}(\log(\alpha_{3k}), \log(\beta_{3k}))$, was set equal to 0.

